#### **8.4.3      Exploratory Endpoint(s)**

The time to next anticancer intervention is defined as the time from randomization to the first anticancer intervention. Those subjects without an anticancer intervention will be censored at their last follow-up assessment when anticancer therapy information is collected.

The time to first opioid use for cancer-related pain is defined as the time from randomization to the first use of an opioid for cancer-related pain. Those subjects without a record of opioid use for cancer-related pain will be censored at their last follow-up assessment when opioid use for cancer-related pain is collected.

The time to first ECOG performance status decline (i.e., increase in numerical value of ECOG performance status) is defined as the time from randomization to the first decline in ECOG performance status by 1 point or more. Those subjects without an ECOG performance status decline will be censored at their last follow-up assessment for ECOG performance status.

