3.4 Data Rules

- *Study Day* = [(visit date) – (date of first infusion [Day 0])]. If the infusion does not occur, Day 0 will be the date of the first leukapheresis, unless it fails, in which case, Day 0 will be the date of registration.
- *Baseline*: baseline is defined as the value closest to but prior to the randomization data.
- *Change from baseline*: change from baseline is the post-baseline value minus the baseline value.
- *Percent change from baseline*: percent change from baseline is calculated as $100 \times (\text{post-baseline value} - \text{baseline value}) / \text{baseline value}$. If the baseline or post-baseline value is missing, then the change from baseline and percent change are set to missing. If the baseline value is zero and the post-baseline is non-zero, then the percent change from baseline is set to missing. If the baseline value is zero and the post-baseline value is also 0, then the percent change from baseline is set to 0.
- *Partial Dates*: Dates missing the day, month and year and the day and month will not be imputed. However, if the month and year are present, the day may be set to the 15th of the month or to a date consistent with a more conservative approach to the analysis of the data point.
- *Missing event or censor date*: If the date of an event or the date of censoring is missing for a time-to-event variable, the last known study date will be used. Subjects who prematurely discontinue from the study before having the event will be censored at their last known alive date.

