4.3 PSA

PSA data, including change from baseline and percent change from baseline, will be summarized descriptively by treatment arm at each time point. For each time point where change from baseline is evaluated for continuous variables, descriptive statistics will be displayed for the values at baseline, values at the time point, values for change from baseline, and percent change from baseline at the time point for the set of subjects who have data at both baseline and the time point being assessed. Additionally, the maximal percent decline of serum PSA from baseline at any time point will be summarized using waterfall plots and will be compared between the treatment groups using a Wilcoxon test. Baseline will be defined as the pre-randomization PSA value. The percent of subjects with a 50% or more maximal decline in PSA at any post-baseline time point will be compared between the treatment arms using a Fisher's exact test.

Time to PSA progression will be compared between the treatment arms using a Cox regression model with terms for treatment, baseline PSA (logarithm scale), and baseline LDH (logarithm scale) in the model based on the ITT population. The estimated HR of the treatment effect and its 2-sided, 95% CI, using the sequential arm as the denominator will be provided. The percentage of subjects free of PSA progression with an associated 95% CI at landmark time points such as 6 and 12 months will be provided by treatment arm as well as pooled over treatment arms using the Kaplan-Meier method.

Time to PSA progression is defined as: 1) the time from randomization to PSA progression, and 2) the time from first enzalutamide treatment to PSA progression. Those subjects who do not experience PSA progression will be censored in the analysis at the date of their last PSA assessment. PSA progression, based on the randomization date (i.e., definition 1) will be defined for those subjects

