4.6.2 Disposition

Subject disposition will be summarized by treatment group for the randomized population. This summary will include, but will not be limited to, the following:

- Number of subjects randomized
- Number of subjects who had at least one leukapheresis
- Number of subjects receiving at least one infusion of sipuleucel-T
- Number of subjects receiving Enzalutamide
- Number of subjects who prematurely discontinued each study treatment
- Reason(s) for premature discontinuation of each study treatment

- Number of subjects who prematurely discontinued the study (i.e., refused further study evaluations [with the possible exception of survival status])
- Reason(s) for premature discontinuation from the study
- Number of subjects who died
- Cause of death summary
- Number of subjects in the immune response, safety analysis, and efficacy analysis sets

In addition, the number of subjects screened for the trial will be summarized.

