4.6.9 Anti-Cancer Interventions and Cancer-Related Opioid Use

All anticancer therapies received prior to screening and through the end of the LTFU phase were collected. Anticancer therapies included, but were not limited to, radiation, chemotherapy, hormone therapy, investigational cancer therapies, all other systemic therapies, and surgery. Each subject's first cancer-related opioid use will be collected and is defined as an opioid used for cancer-related pain that is of at least 2 consecutive days in duration.

The time to next anticancer intervention will be summarized by treatment group and is defined as the time from randomization to the first anticancer intervention as described above. Subjects who do not received any anti-cancer therapies will be censored at the last available contact date. A Cox regression model with treatment arm as the independent variable and stratified by screening PSA levels and screening lactate dehydrogenase will be used to compare the treatment arms with respect to time to first anti-cancer therapy. A similar summary will be produced for the time to first chemotherapy post randomization and time to first cancer-related opioid use.

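### SAP 3.4 censors subjects who leave the study at their last known alive date without limiting the rule to overall survival, which conflicts with, or fills gaps left by, the assessment-based censoring of the other time-to-event endpoints

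*SAP*

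**What the plan says.** SAP 3.3 points to 3.4 for the handling of missing event and censoring dates. The relevant bullet in 3.4 opens "If the date of an event or the date of censoring is missing for a time-to-event variable" and then adds: "Subjects who prematurely discontinue from the study before having the event will be censored at their last known alive date". The second sentence names no endpoint.

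SAP 4.6.2 describes a subject who prematurely discontinued the study as one who "refused further study evaluations [with the possible exception of survival status".

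The endpoint-specific rules are:

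- **PSA progression.** SAP 4.3: "Those subjects who do not experience PSA progression will be censored in the analysis at the date of their last PSA assessment". Protocol 8.4.2 has the same rule.
- **Next anticancer therapy.** Under protocol 8.4.3, subjects without the event "will be censored at their last follow-up assessment when anticancer therapy information is collected". SAP 4.6.9 reads: "Subjects who do not received any anti-cancer therapies will be censored at the last available contact date".
- **First opioid use.** Under protocol 8.4.3, subjects without the event "will be censored at their last follow-up assessment when opioid use for cancer-related pain is collected". SAP 4.6.9 only asks for a summary similar to that for next therapy.
- **ECOG decline.** Protocol 8.4.3: "Those subjects without an ECOG performance status decline will be censored at their last follow-up assessment for ECOG performance status". SAP 2.3 keeps the objective, but SAP 4.6.6 plans only by-visit summaries and shifts.
- **Overall survival.** The opening of SAP section 4 censors at the date last known alive; SAP 4.4 uses the last visit or contact.

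**The concern.** A subject contributes valid event-free time only while someone is looking for the event. Being known alive shows that death has not occurred. It does not show that PSA has not progressed, that performance status has not declined, or that no opioid has been started. If such a subject is censored when last known alive, the stretch after the last relevant assessment enters the risk set with no chance of an event being recorded.

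That pushes Kaplan-Meier event-free estimates up, including the 6- and 12-month PSA landmarks in SAP 4.3. If the arms lose assessments at different rates, it also moves the hazard ratio, in favour of the arm with more drop-out. With 25 and 27 subjects enrolled (SAP 3.1), a few misdated censorings can be visible.

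**Working it through.** No sample size, power or event figure in the documents depends on this rule, so there is no stated figure to reproduce. The check compares the text and then illustrates the size.

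**1. Which rule governs each endpoint**

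| Endpoint | Endpoint-specific rule | Effect of SAP 3.4 |
|---|---|---|
| Overall survival | Last known alive or last contact (SAP 4, 4.4) | Suitable |
| PSA progression | Last PSA assessment (SAP 4.3, protocol 8.4.2) | Conflict, no precedence stated |
| Next anticancer therapy | Protocol: last assessment of therapy use. SAP 4.6.9: last contact | Both SAP rules depart from the protocol |
| First opioid use | Protocol: last assessment of opioid use. SAP 4.6.9: by analogy only | No assessment-based rule in the SAP |
| ECOG decline | Protocol: last ECOG assessment. SAP: none | 3.4 would apply if the protocol's analysis is run |

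**2. Can the two dates differ?** Yes. SAP 4.6.2 allows survival status to be obtained after evaluations are refused. For PSA and ECOG there is a second possible route: notes to protocol Table 1 stop both after one final measurement once enzalutamide ends, and later follow-up is by telephone. A subject who leaves the study after such calls may have been known alive well after the last PSA. The documents do not say how often either happens.

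**3. Size for the 12-month rate.** All inputs here are assumptions: exponential event times with a median of 12 months (true 12-month rate 50%), and a share d of 10%, 20% or 30% leaving in the first year, independently of the event.

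If the gap between last assessment and last known alive is at least 12 months, no drop-out leaves the risk set before month 12. The Kaplan-Meier estimate is then 1 minus the share with an observed event. With departures uniform over the year and λ = ln 2/12:

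- Chance that the event precedes departure = 1 − (1 − 0.5)/ln 2 = 1 − 0.7213 = 0.2787
- Estimate = 1 − [(1 − d) × 0.5 + d × 0.2787] = 0.5 + 0.2213 d
- d = 10%, 20%, 30% gives 52.2%, 54.4%, 56.6%

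A simulation of 400,000 subjects per setting, with departures at a constant rate instead, gives:

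| Gap (months) | d = 10% | d = 20% | d = 30% |
|---|---|---|---|
| 0 (last assessment) | 50.0 | 50.1 | 49.9 |
| 3 | 50.9 | 51.9 | 52.8 |
| 6 | 51.6 | 53.4 | 55.1 |
| 12 or more | 52.3 | 54.7 | 57.0 |

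The last row is the ceiling for this time point, since a longer gap cannot alter the month-12 estimate. With a gap of 12 months or more, the bias is +2.6 to +8.6 points for an 8-month median and +1.7 to +5.5 points for an 18-month median.

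**4. Size for the treatment comparison.** The measure is events divided by follow-up time, with no true difference between arms. With equal drop-out (20% in each arm) the ratio stays at about 1.00 for every gap. For 30% against 10%, with departures continuing to month 36, the ratios and their inverses (the 10% arm over the 30% arm) are:

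- 3-month gap: 0.945, so 1/0.945 = 1.06
- 6-month gap: 0.895, so 1/0.895 = 1.12
- 12-month gap: 0.818, so 1/0.818 = 1.22

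With departures confined to year 1, a 3-month gap gives about 1.04 to 1.06. If all drop-outs are known alive to month 24, the ratio is 1.13, 1.25 or 1.22 with follow-up cut at 12, 24 or 36 months. The 1.25 is the upper case considered, not a mathematical limit. A gap running to the end of 36 months gives 0.685 (1/0.685 = 1.46), but nothing in the documents supports gaps of that length as typical.

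In this trial, 10% of 25 is 2.5 and 30% of 27 is 8.1, so the imbalance means roughly 3 subjects against 8.

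**The case against.** The strongest reply is that the sentence sits in a bullet about missing dates and is best read as a default that gives way to Section 4. On that reading PSA progression follows SAP 4.3 and overall survival is properly served. This largely stands. A reader might infer that the SAP censors every time-to-event endpoint at last known alive, and the documents do not support that. What remains for PSA is two written rules with no statement of which prevails.

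A reader might also infer that the gap routinely runs to years. The documents do not show this. Protocol 4.3.4 and 4.4 follow subjects who withdraw or are lost only through death indexes, and protocol 6.6 lists these as a source for date of death only. No passage treats absence from an index as proof of being alive, so for these subjects last known alive is probably close to the last direct contact.

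For therapy and opioid use, protocol Table 1 collects both at every long-term follow-up visit, including those by telephone. For subjects still followed, last contact and last assessment therefore largely coincide, and the change to SAP 4.6.9 is mainly clarification. It still matters where contact yields survival status alone.

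For ECOG decline, the SAP's table and figure lists contain no time-to-decline analysis, so the issue arises only if the protocol's analysis is run.

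Finally, SAP section 4 calls all analyses descriptive or exploratory. That limits the consequence but does not settle which censoring date to use.

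**Conclusion.** The point holds as a defect of wording and precedence. SAP 3.4 is not limited to overall survival. It conflicts with SAP 4.3 for PSA progression, departs with SAP 4.6.9 from protocol 8.4.3 for next therapy and opioid use, and is the only SAP rule available for ECOG decline.

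Wherever survival is known beyond the last relevant assessment, event-free rates are biased upward. The hazard ratio is also biased if drop-out differs by arm. At a true 12-month rate of 50% with 10% to 30% drop-out, the bias is about 1 to 3 points for a 3-month gap and about 2 to 7 points at the ceiling. The rate ratio under 10% against 30% drop-out is about 1.05 for a 3-month gap and about 1.25 in the upper case considered.

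These sizes rest on assumed drop-out, gap, median and arm imbalance, none of which the documents give. They show sensitivity and do not predict this trial's results. With equal drop-out the comparison is essentially unaffected. The primary endpoint, sample size and power are untouched.

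**What to change.** - In SAP 3.4, limit the last-known-alive sentence to overall survival, and state that endpoint-specific censoring rules take precedence over 3.4.
- Keep SAP 4.3 as it is for PSA progression.
- In SAP 4.6.9, replace the last available contact date with the last assessment at which anticancer therapy was recorded, and give the matching rule for opioid use, as in protocol 8.4.3.
- In SAP 4.6.6, say whether time to ECOG decline will be analysed. If so, censor at the last ECOG assessment.

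The cost is SAP wording only. The assessment dates needed are those of visits already in the schedule. No data collection, sample size or protocol text changes.

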3.5 Visit Windows

Visit based data will be analyzed according to the nominal visit.

In cases where two or more assessments for the same subject have the same nominal visit label, the visit closest in time to the protocol schedule for the visit will be selected for analysis and the other visit regarded as an interim visit. If two visits are equally close in time to the scheduled visit, the visit with the ‘worst-case’ data will be selected. If no time collected, the worst of these assessments will be selected.

4 STATISTICAL METHODS

All analyses will be conducted using SAS Version 9.4 or higher.

Subjects will be stratified by screening PSA levels (≥ 25 ng/mL, yes or no) and screening lactate dehydrogenase (LDH) levels (≥ 200 IU/L, yes or no), both obtained from the central laboratory.

Due to the modification of the sample size for this study, any statistical analyses should be considered descriptive or ‘exploratory.’ Any statistical tests will be performed only to generate hypotheses or for data exploration.

Continuous data will be described using descriptive statistics (i.e., n, arithmetic mean, standard deviation (SD), median, minimum, and maximum). 1st quartile (Q1) and 3rd quartile (Q3) will also be presented. Categorical data will be described using the subject count and percentage in each category. For the summary statistics of all numerical variables unless otherwise specified, minimum and maximum will be displayed to the same level of precision as reported. Mean and median will be displayed to one level of precision greater than the data collected. Standard deviation/standard error will be displayed to two levels of precision greater than the data collected. P-values will be rounded to three decimal places. If a p-value is less than 0.001 it will be reported as “<0.001.” If a p-value is greater than 0.999 it will be reported as “>0.999.”

When count data are presented, the percentage will be suppressed when the count is zero in order to draw attention to the non-zero counts. A row denoted “Missing” will be included in count tabulations where specified on the shells to account for dropouts and missing values. The denominator for all percentages will be the number of subjects in that treatment within the analysis set of interest, unless otherwise specified. No adjustment for multiple comparisons across efficacy or safety variables will be performed.

For each time point where change from Baseline is evaluated for continuous variables, descriptive statistics will be displayed for the values at Baseline, values at the time point, and values for change from baseline at the time point for the set of subjects who have data at both baseline and the time point being assessed.

Any subject receiving a next anti-cancer intervention (as described in section 4.6.9) may have their efficacy observations after the date of that next anti-cancer intervention censored at the earliest date of the next intervention. Overall survival will be assessed censoring at the subjects last-known alive date.

4.1 Product Characterization

Product parameters to be summarized are: CD54 upregulation, CD54⁺ cell count, and TNC count. Product parameters will be summarized descriptively (n, mean [geometric mean], standard error, median, minimum, and maximum) by Infusion (1, 2, and 3) and cumulative (summed across infusions). Cumulative product parameters will be compared between both arms using a Wilcoxon test based on the immune response population. Cumulative CD54 upregulation is the primary endpoint for the study.

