### **8.0 STATISTICAL CONSIDERATIONS**

#### **8.1 General Considerations**

This Phase 2 randomized, open-label study is designed to assess the effects of sipuleucel-T when administered concurrently or sequentially with enzalutamide. Subjects will be randomized 1:1 to either the concurrent arm or the sequential arm, stratified by PSA levels ( $\geq 25$  ng/mL, yes or no) and LDH levels ( $\geq 200$  IU/L, yes or no). In general, data will be summarized in aggregate and by treatment arm. All statistical tests will be performed at the 2-sided 0.05 significance level

unless otherwise noted. Nominal p-values will be provided with no multiplicity adjustment for secondary or exploratory endpoints.

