### **8.5.6.1 Other Analyses**

Use of select anticancer treatments during the study will be summarized by treatment group. This summary will include types of therapies used and will be based on the ITT population.

Data from sipuleucel-T lot release assessments will be summarized. Data to be summarized include CD54 upregulation, CD54+ cell count, and TNC count. These data will be summarized descriptively by infusion (1, 2, and 3) and cumulative (summed across infusions). Cumulative lot release assessment data will be compared between both arms using a t-test on the logarithm scale based on the immune response analysis population.

Prostate specific antigen data, including change from baseline, will be summarized descriptively by treatment arm at each time point for the ITT population. Additionally, the maximal decline of serum PSA from baseline at any time point will be summarized using waterfall plots. Baseline will be defined as the value collected immediately prior to the registration PSA value. Additional analyses of PSA will be performed using the most recent PSA value prior to the initiation of enzalutamide as the baseline value.

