3 STATISTICAL CONSIDERATIONS

3.1 Sample Size Considerations

Approximately 100 subjects will be registered and randomized 1:1 to the Concurrent Arm or the Sequential Arm, with 50 subjects per arm.

PA2024-specific T cell proliferation responses over time will be compared between the concurrent arm and sequential arm using a repeated measurement mixed model analysis. With 43 subjects per arm, there is approximately 90% power to detect a 2-fold difference in mean response between the arms at any time point assuming a coefficient of variation of 1.25. To allow for drop-outs and subjects who may not receive 3 infusions of sipuleucel-T or at least 10 weeks of enzalutamide, approximately 50 subjects per arm will be enrolled.

In the fourth quarter of 2013 Dendreon modified the enrollment goals for this study pursuant to a corporate reorganization plan. Planned enrollment was reduced from 100 subjects to the approximately 50 subjects known to have enrolled at the time of this reorganization. Comparing PA2025-specific T cell proliferation responses over time between the concurrent arm and the sequential are with 25 subjects per arm, there is approximately 70% power to detect a 2-fold difference in mean response between the arms at any time point assuming a coefficient of variation of 1.25. A determination was made that no protocol amendment was required and on February 14, 2014, all participating sites were notified of the decision to stop enrolling subjects. Ultimately, 52 subjects were enrolled: 25 in the Concurrent Arm and 27 in the Sequential Arm

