4.7.2 Final Analysis

The final analysis for this trial will occur when every subject has completed approximately 3 years of survival follow-up. A nominal significance level of 0.05 will be used for all final analyses.

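### SAP 4.1 compares cumulative CD54 upregulation by an unstratified Wilcoxon test with no between-arm ratio or confidence interval, and the PSA-decline and ELISPOT response tests also leave out the PSA and LDH randomization factors

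*SAP*

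**What the plan says.** **Randomization.** SAP 4 states "Subjects will be stratified by screening PSA levels" (cut at 25 ng/mL) and by LDH (cut at 200 IU/L).

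**Analyses that use PSA and LDH.**
- SAP 4.2: the immune-response mixed models carry both stratification factors as covariates.
- SAP 4.3 and 4.4: the Cox models for PSA progression and survival adjust for log PSA and log LDH. Survival also has a stratified log-rank test.
- SAP 4.6.9: the Cox model for next anticancer therapy is stratified by both.

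**Analyses that do not.**
- SAP 4.1, for CD54 upregulation, CD54+ count and TNC: "Cumulative product parameters will be compared between both arms using a Wilcoxon test based on the immune response population". Geometric means and standard errors are planned per arm. No between-arm difference or ratio, and no interval for one, is planned.
- SAP 4.3: maximal percent PSA decline is compared by a plain Wilcoxon test. For the binary version, "The percent of subjects with a 50% or more maximal decline in PSA at any post-baseline time point will be compared" by Fisher's exact test.
- SAP 4.2: ELISPOT response is compared by Fisher's exact test. For proliferation and ELISA the SAP says that responder rates are summarized and that the arms are compared by the ELISPOT methods. Protocol 8.5.3 names Fisher's test for every assay and antigen.

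**The protocol's version.** Protocol 8.5.6.1 says that cumulative lot-release data "will be compared between both arms using a t-test on the logarithm scale". That test was unstratified too.

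**Status of CD54.** SAP 4.1 calls cumulative CD54 upregulation the primary endpoint. SAP 2.1 and Protocol 8.4.1 give that place to PA2024-specific T cell proliferation.

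**The concern.** Two separate things are at issue.

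First, the comparison of a measure labelled primary ends in a p-value. A reader would see two geometric means but not how far apart the arms are or how well that is known. In a trial stopped at 52 subjects and described as exploratory, the estimate and its interval are the most useful output.

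Second, randomizing within PSA and LDH groups balances them between arms. If those groups predict the outcome, the between-arm difference varies less than an unstratified test assumes. The test then rejects too rarely under the null and gives up power. The SAP avoids this in its models but not in these tests, and gives no reason.

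**Working it through.** **Inputs from the documents.** Two-sided 5% level: "All statistical tests will be performed at the 2-sided 0.05 significance level" (Protocol 8.1) and "A nominal significance level of 0.05 will be used for all final analyses" (SAP 4.7.2). Enrolment of 52, as 25 v 27 (SAP 3.1). A 2-fold ratio, "assuming a coefficient of variation of 1.25".

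**Assumptions, not in the documents.** R², the share of log-scale outcome variance explained by the PSA and LDH groups, from 0 to 0.4. Half of subjects above each cut, permuted blocks of 4, a log-normal outcome, all 52 analysed. The CV of 1.25 is the plan's figure for proliferation; none is given for CD54.

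**Step 1: reproduce the plan's power.** SAP 3.1 says "With 43 subjects per arm, there is approximately 90% power to detect a 2-fold difference in mean response", and about 70% with 25 per arm. Log-scale SD = √ln(1 + 1.25²) = 0.970; difference = ln 2 = 0.693.
- 43 per arm: 0.693 / (0.970 × √(2/43)) = 3.31; noncentral t power 90.6%.
- 25 per arm: 0.693 / (0.970 × √(2/25)) = 2.53; power 69.7%.

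Both figures reproduce. They refer to proliferation; no power is stated for CD54, PSA decline or response.

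**Step 2: expected size when the strata are ignored.** With balanced strata the difference has variance reduced by the factor (1 − R²), while the unadjusted standard error is not reduced. Size ≈ 2 × [1 − Φ(1.96 / √(1 − R²))]: 3.9% at R² = 0.1 and 2.8% at R² = 0.2.

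**Step 3: simulation, 6,000 trials per setting, 52 subjects, four strata.**

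| R² | Size: Wilcoxon | Size: van Elteren | Power: Wilcoxon | Power: van Elteren | Power: unadjusted t, log scale | Power: adjusted model, log scale |
|---|---|---|---|---|---|---|
| 0 | 5.0% | 5.0% | 68% | 66% | 71% | 71% |
| 0.1 | 4.0% | 4.8% | 69% | 70% | 72% | 75% |
| 0.2 | 2.6% | 4.7% | 71% | 76% | 74% | 81% |
| 0.3 | 2.3% | 5.2% | 71% | 81% | 75% | 85% |
| 0.4 | 1.5% | 5.1% | 72% | 86% | 76% | 90% |

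The adjusted model has arm, PSA group and LDH group as main effects. Its size stayed between 4.7% and 5.3%.

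**Step 4: separate the two sources of gain.** At R² = 0 the gap between Wilcoxon and the adjusted model (68 v 71%) has nothing to do with strata. It is the price of ranks when the data are log-normal, as simulated, and the unadjusted t-test shows the same 71%. The gain from the strata alone is the last column minus the one before it: about 0, 3, 7, 10 and 14 points.

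**Step 5: effect on an interval.** At R² = 0.2 the mean reported standard error of the log ratio is 0.268 unadjusted and 0.240 adjusted. The actual spread of the estimates is 0.239 and 0.238. The unadjusted estimate is therefore not noisier; its standard error is overstated, by 0.268 / 0.240 = 1.12. At R² = 0 the two standard errors agree (0.267 and 0.268), and adjustment costs 2 degrees of freedom (50 to 48).

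**Step 6: a smaller population.** SAP 4.1 uses the immune response population, whose size is not given. If it lost the 14% implied by 43 of 50, 52 × 0.86 ≈ 45 would remain. At 22 v 23 the unadjusted log-scale t-test has 64.9% power, against 71.4% at 25 v 27.

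**The case against.** The strongest reply is that the loss is conditional. Nothing in the documents says that PSA or LDH group predicts any of these outcomes. CD54 upregulation is measured on the cultured product (Protocol 6.8.2), and no link to serum PSA or LDH is given. At R² = 0 the plain Wilcoxon test keeps its 5% size and beats van Elteren by about 2 points. This stands, so it cannot be said that these tests are conservative, only that they are if R² is above zero. It is not a case for leaving the factors out of a log-scale model, which lost no power at any R² simulated.

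The immune response population is selected after randomization, on 3 infusions and at least 10 weeks of enzalutamide, so stratum balance within it is not guaranteed and the figures for 52 are a best case. This also stands.

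Stronger readings that a reader might infer, and that the documents do not support:
- *Fisher's test shows the cost of ignoring strata.* At 25 v 27 its true size is 2.5 to 3.7% for common rates of 10 to 90%. That comes from the discreteness of the counts and says nothing about strata.
- *PSA decline is the clearest case because PSA is a stratification factor.* SAP 4.3 tests percent decline, which is already scaled to baseline. Whether the 25 ng/mL cut predicts it is not shown.
- *CD54 has no estimate at all.* Geometric means per arm are planned; the contrast and its interval are missing.
- *The SAP dropped a planned adjustment.* The protocol's log-scale t-test had none.
- *A confirmatory conclusion is at risk.* SAP 4 calls every analysis descriptive or exploratory. If proliferation is primary, its mixed model already includes both factors.

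**Conclusion.** The point holds as an improvement to precision and reporting. Two parts need no assumption: no between-arm ratio or interval is planned for cumulative CD54 upregulation, and the tests in SAP 4.1, the PSA-decline tests in SAP 4.3 and the ELISPOT response test in SAP 4.2 leave out factors that the SAP's models use.

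The size of the loss rests on an assumed R². It is nil at 0, about 3 points of power at 0.1, 7 at 0.2 and 14 at 0.4, comparing log-scale analyses with and without the factors. Against the planned Wilcoxon test the differences are about 3, 6, 10 and 18 points, part of which reflects the log-normal outcome assumed. These figures also assume a CV of 1.25 and 52 subjects analysed. No false-positive risk follows: any distortion is towards too few rejections.

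**What to change.** **SAP 4.1.** Analyse the logarithm of cumulative CD54 upregulation, CD54+ count and TNC by a linear model with arm, PSA group and LDH group. Report the ratio of geometric means, concurrent over sequential, with its 95% CI. Keep the Wilcoxon or a van Elteren test as a sensitivity analysis. Enter the two factors as main effects: four cells over at most 52 subjects average 13 or fewer.

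**SAP 4.3.** Compare maximal percent PSA decline by a rank-based or linear model with arm and the two factors. Compare the 50% decline by a Cochran-Mantel-Haenszel analysis over the stratification factors.

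**SAP 4.2.** Use the same Cochran-Mantel-Haenszel approach for ELISPOT response, and say whether response for proliferation and ELISA is tested or only summarized, since Protocol 8.5.3 plans a test for each assay.

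**Primary endpoint.** Reconcile SAP 4.1 with SAP 2.1 and Protocol 8.4.1.

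**Cost.** SAP wording and a few lines of code, with 2 degrees of freedom per model. No extra data are needed, since screening PSA and LDH are already used to randomize.
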